Appendix 3.3. Study and Site Closure

Appendix 3.3.1. Discontinuation of Study Sites

Study site participation may be discontinued if Lilly or its designee, the investigator, or the ERB of the study site judges it necessary for medical, safety, regulatory, or other reasons consistent with applicable laws, regulations, and GCP.

Appendix 3.3.2. Discontinuation of the Study

The study will be discontinued if Lilly or its designee judges it necessary for medical, safety, regulatory, or other reasons consistent with applicable laws, regulations, and GCP.

Appendix 4. Hepatic Monitoring Tests for Treatment-Emergent Abnormality

Selected tests may be obtained in the event of a treatment-emergent hepatic abnormality and may be required in follow-up with patients in consultation with the Lilly, or its designee, clinical research physician.

Hepatic Monitoring Tests

Hepatic Hematology ^a	Haptoglobin ^a
Hemoglobin	
Hematocrit	Hepatic Coagulation ^a
RBC	Prothrombin Time
WBC	Prothrombin Time, INR
Neutrophils, segmented	
Lymphocytes	Hepatic Serologies ^{a,b}
Monocytes	Hepatitis A antibody, total
Eosinophils	Hepatitis A antibody, IgM
Basophils	Hepatitis B surface antigen
Platelets	Hepatitis B surface antibody
	Hepatitis B Core antibody
Hepatic Chemistry ^a	Hepatitis C antibody
Total bilirubin	Hepatitis E antibody, IgG
Direct bilirubin	Hepatitis E antibody, IgM
Alkaline phosphatase	
ALT	Anti-nuclear antibodya
AST	
GGT	Alkaline Phosphatase Isoenzymesa
CPK	
	Anti-smooth muscle antibody (or anti-actin
PK for LY3202626	antibody) ^a

Abbreviations: ALT = alanine aminotransferase; AST = aspirate aminotransferase; CPK = creatinine phosphokinase; GGT = gamma-glutamyl transferase; Ig = immunoglobulin; INR = international normalized ratio; PK = pharmacokinetics; RBC = red blood cells; WBC = white blood cells.

- a Assayed by Lilly-designated or local laboratory.
- b Reflex/confirmation dependent on regulatory requirements and/or testing availability.

Appendix 5. Sampling Summary

This table summarizes the approximate number of samples (venipunctures and lumbar punctures) and volumes for all sampling (screening, standard laboratory, drug concentration, pharmacogenetic, biomarker, and exploratory) and tests during the study. Fewer samples may actually be taken, but this will not require a protocol amendment. Lumbar punctures are only collected for patients participating in the optional substudy.

Protocol I7X-MC-LLCF Sampling Summary

Purpose	Sample Type	Maximum Amount per Sample	Maximum Number Samples	Maximum Total Amount
Screening tests ^a	Blood	3.5 mL	5	14 mL
Standard laboratory tests ^a	Blood	2.5 mL	23	52 mL
Drug, Aβ isoforms, tau	CSF	20 mL	2	40 mL
Drug concentration	Blood	3 mL	12	36 mL
Pharmacogenetic samples	Blood	10 mL	3	27 mL
Other exploratory samples	Blood	10 mL	22	120 mL
Total Blood and CSF				289 mL
Hepatic Monitoringb	Blood	3 - 30 mL	-	-

Abbreviation: CSF = cerebrospinal fluid.

a Additional samples may be drawn if needed for safety purposes.

b Based on laboratory safety values, unscheduled hepatic monitoring testing may be performed as part of patient follow-up, in consultation with Lilly-designated Medical Monitor.

Appendix 6. Protocol Amendment I7X-MC-LLCF(c) Summary Effect of LY3202626 on Alzheimer's Disease Progression as Measured by Cerebral ¹⁸F-AV-1451 Tau-PET in Mild Alzheimer's Disease Dementia

Overview

Protocol I7X-MC-LLCF Effect of LY3202626 on Alzheimer's Disease Progression as Measured by Cerebral ¹⁸F-AV-1451 Tau-PET in Mild Alzheimer's Disease Dementia has been amended. The new protocol is indicated by amendment (c) and will be used to conduct the study in place of any preceding version of the protocol.

The protocol has been amended to include the performance of additional interim analyses and unplanned data reviews by the AC and IRC.

The overall changes and rationale for the specific changes made to this protocol are described in the following table:

Amendment Summary for Protocol I7X-MC-LLCF Amendment (c)

Section # and Name	Description of Change	Brief Rationale
Section 10.3.7 Interim Analyses	Only the AC and Internal Review	Added Interim Review Committee
	Committee (IRC) are is authorized	to permit review of efficacy data
	to evaluate unblinded interim	
	efficacy and safety and efficacy	
	analyses, respectively. Study sites	
	will receive information about	
	interim results ONLY if results are	
	clinically relevant for the safety of	
	their patients. Membership of the	
	AC and IRC will be documented in	
	the AC charter and IRC plan.	
	Unblinding details are specified in	
	the unblinding plan section of the	
	SAP or a separate document.	
Section 10.3.7 Interim Analyses	Details of the timing and decision	Added for clarification
	criteria of the interim Details of the	
	timing and decision criteria of the	
	interim analysis analyses by the AC	
	and IRC are documented in a	
	separate interim analysis plan and/or	
	AC charter in order to maintain	

	study blind, for the primary study team. If an LY3202626 dose may is recommended to be dropped at the interim analysis because of safety and the, then randomization will be modified accordingly; in this instance, the percentage of patients receiving placebo will not be reduced.	
Section 10.3.7 Interim Analyses	An initial safety interim analysis will be conducted by the AC when data from approximately 105 130 qualified patients at 12 weeks and 75 40 patients through 24 weeks have been obtained.	The data from approximately 105 qualified patients at 12 weeks is the data that was intended for safety review by the AC. The data obtained for 75 patients through 24 weeks was intended to support initial pharmacokinetic (PK) model development. As the data from 75 patients with 24 weeks of treatment was not needed to perform the safety review to meet the primary objective, the decision was made to proceed with the data lock with approximately 130 patients with 12 weeks of treatment and 40 patients with 24 weeks of treatment.
Section 10.3.7 Interim Analyses	Efficacy reviews of data by an IRC may occur during the course of the study and will be documented in the IRC plan. At the times specified in Section 10.3.5, a limited number of pre-identified individuals may gain access to the unblinded PK/PD data, as specified in the unblinding plan, prior to the interim or final database lock.	Added to describe efficacy analyses by the IRC
Appendix 1 Abbreviations and Definitions	ICH - International Conference on for Harmonisation	Definition added to the Abbreviations and Definitions Appendix
Appendix 1 Abbreviations and Definitions	IRC – Independent Review Committee	Definition added to the Abbreviations and Definitions Appendix

Revised Protocol Sections

Ī	Note:	Deletions have been identified by strikethroughs.
		Additions have been identified by the use of underscore.

10.3.7. Interim Analyses

Only the AC and Internal Review Committee (IRC) are is authorized to evaluate unblinded interim efficacy and safety and efficacy analyses, respectively. Study sites will receive information about interim results ONLY if results are clinically relevant for the safety of their patients. Membership of the AC and IRC will be documented in the AC charter and IRC plan. Unblinding details are specified in the unblinding plan section of the SAP or a separate document

Details of the timing and decision criteria of the interim analysis analyses by the AC and IRC are documented in a separate interim analysis plan and/or AC charter in order to maintain study blind, for the primary study team. If an LY3202626 dose may is recommended to be dropped at the interim analysis because of safety and the, then randomization will be modified accordingly; in this instance, the percentage of patients receiving placebo will not be reduced.

An initial safety interim analysis will be conducted by the AC when data from approximately 105 130 qualified patients at 12 weeks and 75-40 patients through 24 weeks have been obtained. The AC may be asked to conduct additional safety interim analyses if safety concerns are observed during blinded safety monitoring. In the event that blinded safety monitoring uncovers an issue that needs to be addressed by unblinding at the group level, only members of the AC can conduct additional analyses of the safety data.

Efficacy reviews of data by an IRC may occur during the course of the study and will be documented in the IRC plan. At the times specified in Section 10.3.5, a limited number of pre-identified individuals may gain access to the unblinded PK/PD data, as specified in the unblinding plan, prior to the interim or final database lock. Information that may unblind the study during the analyses will not be reported to study sites or blinded study team until the study has been unblinded.

### 3. Revision History

Statistical Analysis Plan (SAP) Version 1 was approved prior to unblinding.

Statistical Analysis Plan (SAP) Version 2 was approved prior to final database lock. Due to early termination of the study, certain analyses were removed or simplified, while others were clarified. The changes in SAP version 2 are summarized below:

- Clarified that change from baseline to last observation is to be used in ANCOVA analysis if Week 52 observation is not available (Section [5.1](#))
- Removed the exploratory analysis on subjects with study partner change during the study (previously Section 5.11 in Version 1)
- Clarified the analysis for changes from baseline in NPI total score and BASQID total score will be ANCOVA instead of MMRM because they were collected only once during post-baseline visits (Section [5.11.2](#))
- Specified the cut-off for defining Tau subgroups and removed the subgroup analysis regarding race and country (Section [5.11.3](#))
- Removed sensitivity analysis on Tau PET using percentage changes from baseline (previously Section 5.12.4 in Version 1)
- Simplified analysis of CSF biomarkers to listing of values by visit by treatment due to very limited number of subjects participated in the CSF addendum (Section [5.12.2](#))
- Added analysis on annualized change in imaging biomarkers (vMRI, AV-45 PET, AV-1451 PET) because majority of the subjects would not have Week 52 observation due to early termination of the study (Section [5.12.5](#))
- Added an incidence summary for treatment-emergent CSSRS findings (Section [5.13.8.1](#))
- Simplified and clarified the analysis for categorical eye exam and eye imaging data (Section [5.13.8.3](#))

## 4. Study Objectives

### 4.1. Primary Objective

To assess the change from baseline in  $^{18}\text{F}$ -AV-1451 positron emission tomography (PET) after treatment with LY3202626 3 mg or 12 mg per day compared with placebo for 52 weeks among patients with mild Alzheimer's disease (AD) dementia and evidence of brain amyloid.

The endpoint used to assess this will be the change in standardized uptake value ratio (SUVr) of  $^{18}\text{F}$ -AV-1451 PET from baseline to 52 weeks. The change will be compared between the LY3202626 doses (3mg and 12mg) and placebo.

### 4.2. Secondary Objectives

Objectives	Endpoints

Secondary
 
 
To evaluate the safety and tolerability of LY3202626 (3 mg and 12 mg per day) compared with placebo.
 
	
 
Standard safety assessments:               
 
spontaneously reported adverse events (AEs)
 
clinical laboratory tests
 
vital sign and body weight measurements
 
12-lead electrocardiograms (ECGs)
 
physical and neurological examinations
 
 
 
magnetic resonance imaging (MRI; amyloid-related imaging abnormality [ARIA] and emergent radiological findings)
 
Skin examination
 
Eye examination
 
Columbia-Suicide Severity Rating Scale (C-SSRS)
 

 
To assess peripheral pharmacokinetic (PK) and pharmacodynamic (PD) of LY3202626 (3 mg and 12 mg per day) over 52 weeks.
 
To assess change from baseline in cognition after 52 weeks of treatment among patients treated with LY3202626 (3 mg and 12 mg per day) compared with placebo.
 
To assess change from baseline in function after 52 weeks among patients treated with LY3202626 (3 mg and 12 mg per day) compared with placebo.
 
To assess change from baseline in a composite measure of cognition and function after 52 weeks among patients treated with LY3202626 (3 mg and 12 mg per day) compared with placebo.
 
	
 
Plasma PK of LY3202626
 
Plasma PD <math>A\beta_{1-40}</math>, <math>A\beta_{1-42}</math>, <math>A\beta_{1-x}</math>
 
13-item Alzheimer's Disease Assessment Scale – Cognitive subscale (ADAS-Cog13)
 
Alzheimer's Disease Cooperative Study-Activities of Daily Living inventory (ADCS-iADL)
 
integrated Alzheimer's Disease Rating Scale (iADRS)
 

### 4.3. Exploratory Objectives

Objectives	Endpoints

Exploratory
 
 
• To assess change in cognition after 52 weeks among patients treated with LY3202626 (3 mg and 12 mg per day) compared with placebo
 
• To assess change in function after 52 weeks among patients treated with LY3202626 (3 mg and 12 mg per day) compared with placebo
 
• To assess change in cognition after 52 weeks among patients treated with LY3202626 (3 mg and 12 mg per day) compared with placebo
 
• To assess change in everyday functioning after 52 weeks among patients treated with LY3202626 (3 mg and 12 mg per day) compared with placebo
 
• To assess change in neuropsychiatric symptoms after 52 weeks among patients treated with LY3202626 (3 mg and 12 mg per day) compared with placebo
 
• To assess change in subjective quality of life after 52 weeks among patients treated with LY3202626 (3 mg and 12 mg per day) compared with placebo
 
• To assess change from baseline in rCBF after 52 weeks among patients treated with LY3202626 (3 mg and 12 mg per day) compared with placebo.
 
• To assess change from baseline in brain amyloid after 52 weeks among patients treated with LY3202626 (3 mg and 12 mg per day) compared with placebo
 
• To assess change from baseline in brain and brain regional volumes after 52 weeks among patients treated with LY3202626 (3 mg and 12 mg per day) compared with placebo.
 
	
 
• Montreal Cognitive Assessment (MoCA)
 
• Functional Activities Questionnaire (FAQ)
 
• Mini-Mental State Examination (MMSE)
 
• Everyday Cognition (ECog)
 
• Neuropsychiatric Inventory (NPI)
 
• Bath Assessment of Subjective Quality of Life in Dementia (BASQID)
 
• SUVr cerebral perfusion from early post-injection florbetapir PET scan
 
• Florbetapir PET SUVr
 
• Volumetric MRI
 

Abbreviations: MRI = magnetic resonance imaging; PET = positron emission tomography; rCBF = regional cerebral blood flow; SUVr= standardized uptake value ratio.

## 5. A Priori Statistical Methods

### 5.1. General Considerations

All tests of treatment effects of biological efficacy or clinical efficacy will be conducted at a 1-sided  $\alpha=.10$ , unless otherwise stated. Safety assessments will be conducted at a 2-sided  $\alpha=.05$ .

A repeated measures analysis refers to a restricted maximum likelihood (REML)-based, mixed effects repeated measures analysis using all the longitudinal observations at each post-baseline visit.

All analyses will follow the intent-to-treat (ITT) principle unless otherwise specified. An ITT analysis is an analysis of data by the groups to which subjects are assigned by random allocation, even if the subject does not take the assigned treatment, does not receive the correct treatment, or otherwise does not follow the protocol.

When change from baseline is assessed, subjects will be included in the analysis only if both a baseline and a postbaseline measure are available. Unless otherwise defined, Visit 3 is the baseline visit, and baseline value is defined as last value available before or at Visit 3.

All total and subscale scores will be derived from individual items. If any individual item is missing, the corresponding total and subscale scores will be considered missing, except for the ADAS-Cog13 and ADCS-iADL, which will be imputed.

A repeated measures analysis model will include the fixed, categorical effects of treatment, visit, and treatment-by-visit interaction, as well as the continuous, fixed covariates of baseline, baseline-by-visit interaction, and age at baseline.

When an analysis of covariance (ANCOVA) model is used to analyze a continuous efficacy variable, the model will contain the main effects of treatment with baseline value and age at baseline added as covariates. For ANCOVA analysis on change from baseline to Week 52 endpoint, change from baseline to last observation during treatment period will be used if patients do not have Week 52 observation available.

Categorical comparisons between treatment groups will be performed using Fisher's exact tests or logistic regression where appropriate.

Any change to the data analysis methods described in the protocol will require an amendment to the protocol only if it changes a principal feature of the protocol. Any other change to the data analysis methods described in the protocol, and the justification for making the change, will be described in the clinical study report (CSR). Additional exploratory analyses of the data will be conducted as deemed appropriate.

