Patients will initially be randomized into 1 of 3 treatment groups: 2 fixed dose levels of LY3202626 (3 mg and 12 mg per day) and placebo (1:1:1) until approximately 45 participants are enrolled in each arm; then randomization will change to 1:1 with subjects entering either the 12 mg or placebo arm. Treatment duration for all subjects will be 52 weeks.

Number of Patients:

Approximately 380 patients will be enrolled for approximately 320 completed evaluable patients, assuming approximately 15% drop out.

Statistical Analysis:

Patient Characteristics:

Standard baseline characteristics of gender, age, and race will be summarized for all patients. Treatment group comparisons will be made using Fisher's exact test for categorical data and an analysis of variance (ANOVA), with an independent factor for treatment for continuous data. Diagnosis, illness characteristics, and baseline efficacy and safety measures will be analyzed in a similar manner.

Efficacy:

The primary objective of this study is to assess the effect on neuropathological progression of 2 different LY3202626 doses in patients with mild AD dementia compared with placebo, measured by change in ¹⁸F-AV-1451 PET standardized uptake value ratio (SUVr) at baseline and week 52. The primary measurement is change from

baseline ¹⁸F-AV-1451 PET SUVr at Week 52. An analysis of covariance (ANCOVA) will be used to statistically evaluate change in ¹⁸F-AV-1451 PET from baseline at 52 weeks post-dose.

Statistical analyses of mean change in efficacy and health outcome measures will be conducted. Generally, statistical assessment of the efficacy and health outcome measures will be a mixed model repeated measure (MMRM) or an ANCOVA. The primary comparison will be between LY3202626 12 mg versus placebo at endpoint.

Safety:

Safety will be assessed by summarizing and analyzing adverse events (AEs), laboratory analytes, vital signs, electrocardiograms (ECGs), skin examinations, and eye examinations during the treatment period. For continuous safety measurements, a change from baseline will be analyzed using MMRM or ANCOVA model. Safety analyses for the treatment period will include comparisons between LY3202626 dose groups and placebo. All hypotheses will be tested at a 2-sided 0.05 significance level. No adjustments for multiple comparisons will be made.

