Abbreviations: Aβ = amyloid beta peptide; ADAS-Cog₁₃ = 13-item Alzheimer's Disease Assessment Scale – Cognitive subscale; ADCS-ADL = Alzheimer's Disease Cooperative Study-Activities of Daily Living inventory; APOE = apolipoprotein E; BASQID = Bath Assessment of Subjective Quality of Life in Dementia; C-SSRS = Columbia-Suicide Severity Rating Scale; ECG = electrocardiogram; ECog = Everyday Cognition; ED = early discontinuation; EDTA = ethylenediaminetetraacetic acid; FAQ = Functional Activities Questionnaire; MMSE = Mini-Mental Status Examination; MoCA = Montreal Cognitive Assessment; MRI = magnetic resonance imaging; NIA-AA = National Institute on Aging-Alzheimer's Association; NPI = Neuropsychiatric Inventory; PD = pharmacodynamics; PET = positron emission tomography; PK = pharmacokinetics; R&D = research and development; RNA = ribonucleic acid; V = visit.

^a Every effort should be made for visits to occur on the designated study days. The overall treatment period in the protocol should be maintained (that is, visits should be scheduled based on the baseline visit rather than the previous visit). Study procedures designated for a specific visit should be performed within 1 day whenever possible. If the time spent at the site needs to be minimized, the assessments can be completed over a longer period.

- b Visit 1 takes place over more than 1 day. Clinical scales should be administered before imaging procedures are conducted.
- Only capture imaging measures (MRI, florbetapir F 18 PET, and ¹⁸F-AV-1451 PET) at the ED visit if at least 24 weeks have passed since the baseline measurement was obtained. Note: Patients should be encouraged to remain in the study after their ED Visit until Week 52 (Visit 18), even if study treatment has been discontinued. Patients who discontinue treatment, but remain in the study should continue to participate in all scheduled visits and assessments, as appropriate, with the exception of PK measurements and PET scans. The follow-up visit (Week 56) is not required for patients who discontinue study treatment early and continue in the study, unless the study drug was discontinued within that last 4 weeks of the study.
- d Screening period exceeding 60 days will not be considered a protocol deviation. If the screening period exceeds 120 days, sites should contact the Lilly-designated medical monitor for guidance.

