Patients who discontinue study treatment early should receive all early discontinuation procedures as described in Section 2. Patients should be encouraged to remain in the study until Week 52 (Visit 18), even if study treatment has been discontinued, and they should continue to participate in scheduled visits as described in Section 2. Patients who agree to remain in the study after discontinuing study treatment should continue to participate in scheduled visits and assessments, as appropriate, with the exception of PK measurements and PET scans, after completing the early discontinuation assessments described in Section 2, as appropriate. The follow-up visit (Week 56) is not required for patients who discontinue study treatment early and continue in the study, unless the study drug was discontinued within that last 4 weeks of the study. The Lilly-designated medical monitor may be consulted regarding the details of managing a specific patient who discontinues treatment but remains in the study.

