9.1. Efficacy Assessments

9.1.1. Primary Outcome Assessments

¹⁸F-AV-1451 PET. ¹⁸F-AV-1451 PET scans provide an in vivo measurement of the anatomical distribution and load of paired-helical filament (PHF)-tau pathology in the brain (Xia et al. 2013). Along with amyloid plaques, tau PHF tangles are one of the defining pathological signatures of neuropathologically confirmed AD. Elevated ¹⁸F-AV-1451 binding is increased in AD relative to control subjects and presents in an anatomical distribution consistent with neuropathological Braak staging (Chien et al. 2013). In contrast to amyloid, which becomes elevated many years before the onset of clinical symptoms, tau pathology is more closely associated in time with cognitive and functional decline. The ¹⁸F-AV-1451 assessment involves 2 PET scans, one at baseline and another after 52 weeks of treatment (or upon early discontinuation). The change in ¹⁸F-AV-1451 SUVr between the two PET scans will be the primary outcome measure. The change in ¹⁸F-AV-1451 SUVr will be compared across the treatment groups and to total exposure to LY3202626.

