## **5.11. Efficacy Analyses**

### **5.11.1. Primary Outcome and Methodology**

The primary objective of this study is to assess the PD effect of 2 different LY3202626 doses (3 mg and 12 mg) in patients with mild AD dementia compared with placebo, measured by change from baseline in 18F-AV-1451 PET SUVrs at Week 52.

The primary statistical analysis is the ANCOVA, which will be used to statistically evaluate change in composite SUVr from baseline at 52 weeks post-dose. The ANCOVA will include the fixed, categorical effects of treatment dose, and the continuous, fixed covariate of baseline Tau PET SUVr and age at baseline.

Change from baseline analyses will be conducted on SUVrs computed from the following 3 composite regions with the bimodal white matter serving as the reference region: MUBADA (primary), Delta\_Z, and the frontal lobe region defined as a weighted average (weights being the number of voxels in the region) of SUV counts, averaged bilaterally, in the following Region of Interests (ROIs):

- cingulum anterior
- Inferior frontal gyrus, opercular part
- Inferior frontal gyrus, orbital part
- Inferior frontal gyrus, triangular part
- Middle frontal gyrus
- Middle frontal gyrus, orbital part
- Superior frontal gyrus
- Superior frontal gyrus, medial
- Superior frontal gyrus, orbital part

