### **5.12.5. Analyses of Volumetric MRI Data**

Brain atrophy is one of the signature biological changes associated with AD, with shrinkage of the medial temporal lobe (including the hippocampus) and ventricular enlargement particularly prominent. The volume of different brain structures and measures of atrophy can be accurately quantified from vMRI scans. Magnetic resonance imaging changes in brain volume from baseline to after 52 weeks of treatment (or early discontinuation) will be quantified. Measurements of brain structural changes, including, but not limited to, whole brain, ventricles and hippocampus will be evaluated. Brain structural changes will be compared across treatment groups and to total exposure to LY3202626.

Analyses of the following vMRI parameters will be conducted:

- Right hippocampal volume ( $\text{mm}^3$ )
- Left hippocampal volume ( $\text{mm}^3$ )
- Right hippocampal volume ( $\text{mm}^3$ ) + Left hippocampal volume ( $\text{mm}^3$ )
- Right entorhinal cortex ( $\text{mm}^3$ )
- Left entorhinal cortex ( $\text{mm}^3$ )
- Atrophy of Total whole brain volume ( $\text{cm}^3$ )
- Enlargement of Ventricular volume ( $\text{cm}^3$ )

To evaluate the changes in vMRI data after treatment, an ANCOVA model will be used to compare change from baseline to 52 weeks. The change from baseline to the endpoint visit will be the dependent variable. The model for the fixed effects will include terms for the following independent effects: baseline vMRI value, age at baseline, and treatment.

In addition, annualized change in imaging biomarkers (vMRI, AV-45 and AV-1451) for each patient will be calculated using the change at the last post-baseline visit. The annualized change will be compared among the treatment groups with the same ANCOVA model described above.

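### Using the last AV-1451 scan as the Week 52 value, with no term for scan interval or randomization phase, can bias the primary 3 mg versus placebo contrast against 3 mg; the size depends on accrual and may be zero.

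*SAP*

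**What the plan says.** - **Endpoint.** The primary objective (SAP 4.1) compares AV-1451 SUVr change to 52 weeks between each dose and placebo.
- **Substitution.** SAP 5.1 states for this ANCOVA that "change from baseline to last observation during treatment period will be used if patients do not have Week 52 observation available". SAP Section 3 explains that the "majority of the subjects would not have Week 52 observation due to early termination of the study".
- **Model.** Besides treatment, SAP 5.11.1 includes "the continuous, fixed covariate of baseline Tau PET SUVr and age at baseline". It has no term for scan interval or randomization phase. Phase is not a stratification factor either (Protocol 7.2).
- **Scan timing.** Protocol 9.1.1 allows the second scan at Week 52 or at early discontinuation. Footnote c to the Schedule of Activities (Protocol Section 2) has imaging captured "at the ED visit if at least 24 weeks have passed since the baseline measurement was obtained". Under Protocol 8.1.1, patients who stop treatment but stay in the study continue "scheduled visits and assessments, as appropriate, with the exception of PK measurements and PET scans".
- **Allocation.** The Protocol Synopsis sets 1:1:1 "until approximately 45 participants are enrolled in each arm; then randomization will change to 1:1", for 12 mg and placebo only. Protocol 5.1 plans about 167, 167 and 45 patients for placebo, 12 mg and 3 mg.
- **Partial remedy.** SAP 5.12.5 adds that "annualized change in imaging biomarkers (vMRI, AV-45 and AV-1451) for each patient will be calculated using the change at the last post-baseline visit", using the same ANCOVA.

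**The concern.** A rule meant for occasional dropouts now supplies most of the primary data, at scan times that vary by up to 28 weeks (24 to 52). Protocol 3.2 says the tau signal increases as disease progresses, so a longer interval means more SUVr rise whatever the treatment. By plan, every 3 mg patient comes from the first randomization phase, against 45/167 = 27% of placebo patients. At a common stop date the average 3 mg interval is therefore equal to or longer than placebo's, other things being equal.

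The model cannot separate that gap from treatment. Enrolment timing alone could hide a 3 mg benefit, make 3 mg look worse than placebo, or distort the apparent dose response.

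**Working it through.** **1. The plan's own figures.** 167 + 167 + 45 = 379, against about 380 randomized. 380 × 0.85 = 323, against about 320 completers. Both agree. The first phase is 3 × 45 = 135 patients and the second about 379 − 135 = 244.

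**2. Assumptions not in the documents.** Uniform accrual; one stop date for all; scans at termination follow the 24-week early-discontinuation rule; linear SUVr change; no other dropout.

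For a patient enrolled at week *e* with the stop at week *T*, the interval is min(52, *T* − *e*), counted if at least 24. Bias as a share of the 52-week placebo change = (mean 3 mg interval − mean placebo interval)/52.

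**3. One case in full: accrual over 52 weeks, stop at week 65.**
- Rate 379/52 = 7.29 per week; the first phase ends at week 135/7.29 = 18.5.
- First phase: entrants to week 13 have 52 weeks; the rest run from 52 down to 46.5, mean about 49.2. Mean = (13 × 52 + 5.5 × 49.2)/18.5 = 51.2 weeks. This is the 3 mg mean.
- Second phase with a scan: entered weeks 18.5 to 41, intervals 46.5 down to 24, mean 35.2. Placebo number = 22.5 × 7.29/2 = 82.
- Placebo mean = (45 × 51.2 + 82 × 35.2)/127 = 40.9 weeks.
- Bias = (51.2 − 40.9)/52 = 10.3/52 = 0.20.
- Share at Week 52 = 13 × 7.29/379 = 25%, consistent with most patients lacking it.

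**4. Other cases.**

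| Accrual (weeks) | Stop (week) | Mean 3 mg | Mean placebo | Bias/52-week change |
|---|---|---|---|---|
| 52 | 65 | 51.2 | 40.9 | 0.20 |
| 104 | 78 | 50.4 | 43.1 | 7.3/52 = 0.14 |
| 104 | 91 | 52.0 | 44.8 | 7.2/52 = 0.14 |
| 104 | before 61 | equal | equal | 0 |

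The last row follows from 379/104 = 3.64 per week: the first phase ends at week 135/3.64 = 37, and no second-phase patient reaches 24 weeks before week 37 + 24 = 61.

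**5. The one timing clue.** Protocol 10.3.7 and Appendix 6 describe a lock with about 130 patients at 12 weeks and 40 at 24 weeks. If those counts track enrolment, the end of the 135-patient first phase stood near week 12. Second-phase patients would then reach 24 weeks about 24 − 12 = 12 weeks later. A stop within about 12 weeks of that lock gives roughly zero bias.

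**6. SD units (these figures exclude the zero-bias cases).** The design effect is redacted. Back-solving from the stated 79% power at 30% dropout, with 167 × 0.70 = 117 per arm and 1-sided 0.10: (1.282 + 0.806) × √(2/117) = 0.273 SD. If that is 25–50% slowing, the 52-week placebo change is 0.273/0.50 = 0.55 to 0.273/0.25 = 1.09 SD. Simulating the SAP model with no drug effect, in settings with interval gaps of about 6–10 weeks (2,000 runs each):

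| Analysis | Mean estimate (SD) | Rejection for benefit (nominal 0.10) |
|---|---|---|
| 3 mg, as written | +0.07 to +0.21 | 0.008–0.053 |
| 3 mg, phase term added | −0.006 to +0.007 | 0.102–0.124 |
| 3 mg, annualized change | −0.007 to +0.005 | 0.074–0.096 |
| 12 mg, as written | −0.003 to +0.003 | 0.091–0.105 |

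**7. 12 mg.** Allocation to 12 mg and placebo is equal in both phases, so intervals balance. A treatment difference that grows linearly shrinks by 1 − mean interval/52. In the step 3 case that is 1 − 40.9/52 = 21%; it is about 12–34% over the wider range of accrual patterns assumed.

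**The case against.** The strongest reply is that the sponsor saw the problem. SAP version 2 adds the annualized AV-1451 analysis expressly because of early termination, and under linear change it removes the 3 mg bias. The Synopsis and Protocol 10.3.3.2 make 12 mg versus placebo the primary comparison for efficacy measures, and that contrast keeps its type I error. Protocol 3.2 makes safety the main focus for 3 mg. The bias is also conservative: it cannot create a false 3 mg benefit.

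All of this stands and lowers the priority. It does not clear the 3 mg contrast. That contrast is in the primary objective, and the annualized analysis is additional, sits under volumetric MRI and leaves SAP 5.11.1 unchanged. It also assumes linearity and gives short, noisier intervals equal weight. The per-protocol analysis is a weak check: SAP Table 1 requires the primary endpoint at every scheduled visit, so few patients may qualify.

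A reader might go further and infer that the 3 mg result is certainly biased by a known amount, or that the whole primary analysis is invalid. The documents support neither. They give no accrual dates, stop date or arm sizes at termination, the bias may be zero, and 1:1 allocation protects the 12 mg test under the null.

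**Conclusion.** Wrong as written for 3 mg versus placebo, conditional on accrual; minor to moderate priority. The direction, if any bias exists, is against 3 mg. Its size lies between 0 and about 0.20 of the 52-week placebo change, given a common stop date, scans only from 24 weeks, linear change and the accrual patterns assumed. It is zero if no second-phase patient had reached 24 weeks.

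For 12 mg, the test is sound under the null. The estimate is an attenuated average over mixed durations and should not be read as a 52-week effect.

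**What to change.** Blinded staff should make and date these changes in SAP 5.11.1 before final database lock, because Protocol 10.3.7 permits unblinded efficacy reviews by the Internal Review Committee:

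1. Compare 3 mg with placebo patients randomized during the 1:1:1 phase (preferred). Scan intervals then balance by randomization, whatever the shape of change over time. Alternatively, add randomization phase to the ANCOVA. That assumes equal treatment effects in both phases and can leave about 0.01–0.03 SD against 3 mg if only 12 mg works.
2. Name the annualized AV-1451 ANCOVA of SAP 5.12.5 as the accompanying analysis for reading the 3 mg result.
3. Report scan intervals by arm, and label the last-observation result *change to last scan*.

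No new data are needed. The cost is precision for 3 mg. In simulations with accrual rates suggested by the documents and 10–40% of patients at Week 52 (zero-bias cases again excluded), the SD of the estimate is 0.17–0.19 as written, 0.19–0.20 with the phase term and 0.20–0.22 with first-phase placebo only. The change departs from the ANCOVA in Protocol 10.3.3.1 and needs justification in the clinical study report, as SAP 5.1 provides. Phase is fixed by randomization date, so defining it needs no outcome data. The 12 mg analysis can stay as written.
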